**Table 1: Symbols and definitions of terms used in parasite clearance analysis (Part 1)**

Symbol	Definition
$PRR_{48,i}$	Individual specific Parasite Reduction Ratio per 48 h
$PRR_{48,D}$	Dose specific Parasite Reduction Ratio per 48 h
$\beta_{1,i}$	Slope coefficient of $\log_{10}$ parasitaemia vs. time profile for individual $i$
$SE_{\beta_{1,i}}$	SE corresponding to $\beta_{1,i}$ for individual $i$
$\bar{\beta}_{1,D}$	Dose specific average slope estimate
$SE(\bar{\beta}_{1,D})$	Weighted SE of dose specific average slope estimate
$PCt\%$	Parasite clearance half-life

#### Regression Modelling to Determine Optimal Fit

A regression modelling approach to remove potential lag and/or tail phases of the parasitaemia decay profile will be used to determine the optimal log-linear decay regression. The algorithm considers removing parasitaemia data points in an iterative process from both ends of the parasitaemia curve, i.e. a combination of right censoring (removing values from the tail phase) and left censoring (removing values from the lag phase), and uses model selection techniques to find the optimal log-linear regression.

The algorithm to obtain the log-linear decay for each participant is based on the log-linear regression detailed in Equation (1), where Time is the number of hours since administration of antimalarial treatment ( $Time = 1, \dots, m$ ), and  $\beta_0$  and  $\beta_1$  are the intercept and slope estimates, respectively.

$$\log_{10} Parasitemia = \beta_0 + \beta_1 Time \quad (1)$$

Based on the parasitaemia data for each participant, the iterative algorithm to determine the optimal log-linear decay for each participant is summarised in Table 2. The iterative algorithm is continued until a minimum of four observations are available.

The optimal log-linear regression model for a participant is deemed an appropriate fit if the overall model p-value  $< 0.001$ .

**Table 2: Iteration process to determine the optimal log-linear decay curve.**

Step 1: For each participant, fit the full model - fit a linear regression (as defined by Equation 1) to all  $m$  parasitaemia values of participant  $i$

Step 2: Fit two models:

- (a) Fit linear regression model to  $m - 1$  parasitaemia values, removing the first observation.
- (b) Fit linear regression model to  $m - 1$  parasitaemia values, removing the last observation.

Step 3: Determine the best model of Step 2(a) and Step 2(b), defined as the model corresponding to the minimum overall model p-value.

Step 4: Of the best model defined in Step 3, repeat Step 2 and Step 3 in an iterative process until a minimum of four observations.

Step 5: Of the  $m - 3$  best models selected per iteration (including the full model (Step 1)), the optimal model was defined by the minimum overall model p-value.

### Estimating Participant Specific PRR

The slope and corresponding SE estimate of the optimal linear regression model is used to calculate the participant specific  $PRR_{48}$  estimate and corresponding 95% confidence interval (95% CI), as shown in Equation (2) and (3), respectively.

$$PRR_{48,i} = 10^{-48 \times \beta_{1,i}} \quad (2)$$

$$95\% \text{ CI: } 10^{-48(\beta_{1,i} \pm 1.96 \times SE(\beta_{1,i}))} \quad (3)$$

where  $\beta_{1,i}$  and  $SE_{\beta(1,i)}$  are the slope and corresponding standard error of the slope parameter of the optimal linear regression model, respectively.

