#### 4. STATISTICAL CONSIDERATIONS

Data analysis will be performed according to the Sponsor's representative Standard Operating Procedures (SOPs).

The general analytical approach for all endpoints will be descriptive in nature. All summaries will present the data by dose group as well as by all participants combined.

Unless otherwise stated, the following statistical approaches will be taken:

Continuous variables:	Descriptive statistics will include the number of non-missing values, mean, standard deviation (SD), CV%, median, interquartile range, minimum, and maximum. The minimum and maximum values will be presented to the same number of decimal places as recorded in the raw data; mean and median will be presented to 1 decimal place more than raw data; and SD will be presented to two more decimal places than the raw data. The number of decimals for lab parameters may be reduced if the full presentation of the data includes more than 4 significant figures.
Categorical variables:	Descriptive statistics will include frequency counts and percentages per category. Percentages will be rounded to one decimal place, with the denominator being the number of patients in the relevant population.
Imputation:	No imputation will be performed for missing data.
Confidence intervals (CIs):	CIs will be two-sided and will use 95% confidence levels.
Unscheduled Visits	Unscheduled visits that do not have laboratory data on the same visit date will be excluded from summary tables.
Early termination visit	Assessments conducted at Early Termination will be excluded from visit-based summary tables unless otherwise indicated.

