#### 11.1.2 Parasite clearance kinetics

The Parasite Reduction Ratio (PRR) and corresponding parasite clearance half-life ( $PCt_{1/2}$ ) of asexual parasites is derived from the clearance rate of parasitaemia after administration of MMV367 treatment. The analysis of PD response to investigational antimalarial therapy consists of:

- calculating the optimal parasite clearance rate (slope coefficient from the log-linear decay regression of qPCR data) for each individual, then,
- estimating dose specific parasite clearance rate and 95% confidence interval (CI) by calculating the weighted average slope estimate and corresponding standard error (SE) using an inverse-variance method.

The data used for all model selection and fitting calculations is comprised of the  $\log_{10}$  transformed geometric mean of parasitaemia per time point per participant up to the first time point all parasitaemia replicates are ND. If during initial parasite clearance there are no samples ND for a participant, the last time point included in the analyses will be three time points after the minimum observed parasitemia value. All subsequent time points are set to 'missing' regardless of whether parasitaemia values increased afterwards due to potential

recrudescence. Sensitivity analyses may be performed using other thresholds to determine parasite clearance, for example, but not limited to, the lower limit of quantification (LOQ) (i.e. the lower limit of the reportable range) of 32 parasites/mL or limit of detection of 111 parasites/mL [1], to assess robustness of PRR estimates.

The PRR per 48 hours,  $PRR_{48}$ , for asexual parasite will be estimated using the slope of the optimal fit of the log-linear relationship of the parasitaemia decay over time from MMV367 administration for each individual, as detailed in CTM QIMR SOP 41 and Marquart et al. [2]

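### The participant-level 95% CI for PRR48 in SAP Eq. (3) uses 1.96 with the SE of a small, p-value-selected regression, so it covers less than 95%; use the t quantile and state that the limits are conditional on the selected window

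*SAP*

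**What the plan says.** SAP 11.1.2 fits a straight line to log10 parasitaemia against time for each participant, with one geometric mean per time point, "up to the first time point all parasitaemia replicates are ND". Table 2 then drops points from either end. At each step it keeps the fit with the smaller p-value, and at the end "the optimal model was defined by the minimum overall model p-value". On how far trimming may go: "The iterative algorithm is continued until a minimum of four observations are available".

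The slope and SE of the chosen fit go straight into Eqs. (2) and (3): "The slope and corresponding SE estimate of the optimal linear regression model is used to calculate the participant specific" PRR48 and its interval. Eq. (3) multiplies the SE by a fixed 1.96 and labels the result a 95% CI. SAP section 4 sets the general standard: "CIs will be two-sided and will use 95% confidence levels".

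There is one fit rule: "The optimal log-linear regression model for a participant is deemed an appropriate fit if the overall model p-value" is below 0.001. The SAP applies it to decide who enters the dose-level average. Neither document gives a t quantile, a degrees-of-freedom term, a bootstrap or any other allowance for choosing the window. The optional sensitivity analyses in 11.1.2 vary only the clearance threshold. The SAP cites an SOP and a methods paper for details, but it prints the interval formula itself.

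**The concern.** Slope ± 1.96 × SE is a 95% interval when the residual variance is known, or estimated from many points, and the window was fixed beforehand. Neither condition holds here. The residual variance comes from a handful of points, so the reference distribution is t on n-2 df. The window is the one that makes the line look most significant, so the SE tends to be understated. Any lag or tail points that survive trimming shift the slope itself.

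PRR48 is a named secondary endpoint. Cohort 1 puts 3, 2 and 1 participants on its three doses. Where a dose has one fitted participant, Eqs. (4) to (6) reduce to Eqs. (2) and (3), so the individual interval is also the dose-level interval.

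**Working it through.** **1. The SAP's multiplier.** The two-sided 95% normal quantile is 1.95996, so 1.96 is reproduced as a normal quantile.

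**2. How many points to expect.** The protocol's dose justification predicts a median log10 PRR48 of 2.9 (20 mg) and 3.6 (90 mg). Assume a starting level of 10^4.3/mL and a detection limit of 10/mL; these values are assumptions. The fall to the limit is then 4.3 - 1.0 = 3.3 log10.
- At 2.9: 3.3 / (2.9/48) = 54.6 h. PCR times from pre-dose to 54 h give 11 points.
- At 3.6: 3.3 / (3.6/48) = 44 h. PCR times from pre-dose to 36 h give 9 points.

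**3. Quantile alone, window fixed in advance.** Coverage of ±1.96 SE is 2·F(1.96; n-2) - 1, where F is the t distribution function. The correct multiplier is t(0.975; n-2).

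| n | t multiplier | ratio to 1.96 | coverage of Eq. (3) |
|---|---|---|---|
| 4 | 4.303 | 2.20 | 81.1% |
| 6 | 2.776 | 1.42 | 87.8% |
| 8 | 2.447 | 1.25 | 90.2% |
| 10 | 2.306 | 1.18 | 91.4% |
| 13 | 2.201 | 1.12 | 92.4% |

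Given independent normal errors, this step does not depend on the size of the noise.

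**4. With the Table 2 selection.** The algorithm was simulated on the protocol's PCR times with the assumptions in step 2, independent log10 errors with SD 0.15 to 0.30, and no ND value kept.
- No lag, log10 PRR48 2.9 to 5.0: Eq. (3) covers about 85-92%. With t(n-2) instead, about 90-95%.
- Assumed 2 h lag: 84-89%.
- Assumed 6 h lag, log10 PRR48 2.9 to 3.6: about 60-80%. With t(n-2), about 76-88%. Mean bias is about -0.16 to -0.33 log10 PRR48, while the true SD of the slope is only 1.1 to 1.3 times the reported SE.
- A four-point window was chosen in at most 0.3% of these runs.

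**5. Other assumptions.**
- Log-linear decay, 8 to 13 points, SD 0.2 to 0.5: Eq. (3) covers 77-92%. The low end is 8 points with the highest noise. Four-point windows were chosen in 0-6% of profiles.
- First all-ND time point kept at 1 parasite/mL, SD 0.2 to 0.5: 77-86% without a lag and 82-92% with a 6 h lag. Here the ND value introduces its own bias, which offsets part of the lag bias.
- A 6 h lag plus a tail plateau at 10^1.5/mL: 12-58%, mostly slope bias.

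Eq. (3) after selection did not reach 95% in any setting.

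**6. Flat profiles.** With no true clearance, 8 to 15 points and SD 0.3, the Eq. (3) interval excludes PRR48 = 1 in 57-72% of profiles if no fit rule is applied. Requiring p < 0.001 as well leaves about 1-3%.

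**The case against.** The strongest case on the other side is about size and consequence.

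- **Four points is a floor, not the norm.** A reader might infer from the floor that intervals are typically off by a factor of 4.30/1.96. Minimum-p selection tends to keep long windows, and at 9 to 11 points the t multiplier is 2.37 to 2.26. This objection stands.
- **The lag figures are largely bias.** A reader might take 60-80% as showing intervals that are far too narrow. No lag duration is documented, the result changes with the ND handling, and the bias belongs to the point estimate. This stands, and it is why a wider interval is only a partial repair.
- **Flat profiles.** A reader might infer that the plan would declare clearance in most participants who have none. The SAP never uses Eq. (3) to test PRR48 = 1, and its own fit rule marks nearly all such profiles as inappropriate. One reservation remains: the SAP does not expressly withhold Eq. (3) from failed fits, and 11.1.3 presents PD parameters for everyone in the PD population.
- **Little hangs on it.** SAP section 4 describes the analysis as descriptive, no decision rule uses Eq. (3), and 11.1.3 does not mention individual CIs among the listed outputs. The t quantile adds only about 0.04 to 0.15 log10 PRR48 to the half-width. This limits the importance but does not make the 95% label correct.
- **A lag-plus-line model is no clean replacement.** The SAP's algorithm also targets a tail phase. With the assumed plateau, a lag-only model covered 0-9%. Its limits would also sit around a Table 2 estimate from a different model. This stands and narrows the fix.

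**Conclusion.** Eq. (3) is wrong as written. The t quantile is the correct one for a fixed window, and 1.96 falls short of 95% at every window size the schedule allows: about 90-92% at 8 to 13 points and 81% at the rare four-point floor. Choosing the window by minimum p-value lowers coverage to about 85-92% in the no-lag case, and further with few points, high noise or a lag. The first figures rest only on the regression model with independent normal errors. The simulated figures rest on assumed noise, starting level, detection limit and lag, none of which the documents give.

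The documents do not support reading this as a threat to the primary endpoint, which is analysed by separate PK/PD modelling. The point is worth correcting because the label is wrong and the repair is simple.

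**What to change.** 1. In Eq. (3), replace 1.96 by the t quantile on n-2 df, with n the number of points in the participant's selected window, and list n beside the interval. Where a dose has a single fitted participant, let the dose-level interval carry the same limits, so that one slope is not given two intervals.
2. State in the SAP and the report that these limits are conditional on the selected window and remain below nominal coverage.
3. As a sensitivity analysis, report either a bootstrap interval that reruns Table 2 in each resample, or a model with both lag and tail segments reported with its own point estimate. Do not put that model's limits around the Table 2 slope. A simple pairs-percentile bootstrap covered 100% in 150 runs per setting, so it should be described as conservative.
4. State whether Eq. (3) is reported for participants who fail the p < 0.001 rule, and flag those fits if it is.

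The cost is SAP wording and a few lines of R. Individual intervals widen by about 15-21% at 9 to 11 points (2.262/1.96 = 1.15; 2.365/1.96 = 1.21). The main point estimates do not change and no new data are needed.

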### Estimating Dose Specific PRR (PRR48,D)

Of the participants with appropriate overall fit ( $p < 0.001$ ), the average  $PRR_{48}$  and corresponding 95% CI for each cohort is estimated by using the inverse variance method to calculate the weighted average linear regression slope ( $\bar{\beta}_1$ ) and corresponding SE. The weighted average slope for  $s$  participants in the dose with appropriate overall fit is given by Equation (4):

$$\bar{\beta}_1 = \frac{\sum_{i=1}^s (w_i \times \beta_{1,i})}{\sum_{i=1}^s w_i}, \quad i = 1, \dots, s \quad (4)$$

where the weight is the inverse of the squared standard error,  $w_i = \frac{1}{SE(\beta_{1,i})^2}$ . The standard error of  $\bar{\beta}_1$  is estimated as,  $SE(\bar{\beta}_1) = \sqrt{\frac{1}{\sum_{i=1}^s w_i}}$ .

Therefore the dose specific PRR (PRR48,D) and corresponding 95% confidence interval is estimated as shown in Equation (5) and (6), respectively:

$$PRR_{48,D} = 10^{-48 \times \bar{\beta}_1} \quad (5)$$

$$95\% \text{ CI: } 10^{-48 \times (\bar{\beta}_1 \pm 1.96 \times SE(\bar{\beta}_1))} \quad (6)$$

PRR48 estimates will also be reported as  $\log_{10}(PRR_{48})$ .

### Parasite Clearance Half Life

The parasite clearance half-life ( $PCt_{1/2}$ ) will be derived from the optimal decay rate, as shown in Equation (7):

$$PCt_{1/2} = \frac{\log_{10}(2)}{-\beta_1} \quad (7)$$

The relationship between  $PRR_{48}$  and parasite clearance half-life ( $PCt_{1/2}$ ) is a simple transformation of the  $PRR_{48}$  as shown in Equation (8):

$$PCt_{1/2} = \log_{10}(2) \times \left( \frac{48 \text{ hours}}{\log_{10}(PRR_{48,i})} \right) = \frac{\log_{10}(2)}{-\beta_{1,i}} \quad (8)$$

where  $PRR_{48,i}$  is the parasitaemia ratio estimated over a 48-hour interval that is subsequently transformed into a per hour clearance rate.

#### Comparison of Dose Specific $PRR_{48}$

To determine whether there are differences between dose specific PRRs, an omnibus test for between group differences is used. The test is used to assess whether there are differences in the weighted mean slope of the  $J$  doses, using the test statistic shown in Equation (9),

$$Q_B = \sum_{j=1}^J w_j \cdot (\bar{\beta}_{j\cdot} - \bar{\beta}_{\cdot\cdot})^2 \sim \chi_{J-1}^2 \quad j = 1, \dots, J \quad (9)$$

The weight for the  $j^{th}$  dose is denoted by  $w_j = \sum_{i=1}^{s_j} w_{ij}$  for participant  $i$  with appropriate overall fit in dose  $j$ . The  $\bar{\beta}_{j\cdot}$  is the weighted average slope for dose  $j$  as defined in Equation (10), and  $\bar{\beta}_{\cdot\cdot}$  is the weighted grand mean given by:

$$\bar{\beta}_{\cdot\cdot} = \frac{\sum_{j=1}^J w_j \bar{\beta}_{j\cdot}}{\sum_{j=1}^J w_j} \quad (10)$$

Post-hoc pair-wise comparisons can be calculated using the test statistic  $Z_G = \frac{G}{\sqrt{v_G}}$ , where  $G$  is the contrast ( $G = c_1 \bar{\beta}_{1\cdot} + \dots + c_j \bar{\beta}_{j\cdot}$ ) and  $v_G$  is the variance of the contrast ( $v_G = \frac{c_1^2}{w_{1\cdot}} + \dots + \frac{c_j^2}{w_{j\cdot}}$ ). The p-value of the  $L$  pair-wise comparisons can be calculated using the Scheffe method, by comparing  $Z_G^2$  to a chi-squared distribution with  $L - 1$  degrees of freedom.

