Parasite regrowth following initial parasite clearance is required to effectively characterise PK/PD parameters such as the half maximum effective concentration (EC_{50}) of MMV367. A single dose of 20 mg is expected to result in initial parasite clearance in the IBSM model (\log_{10} parasite reduction ratio over a 48 h period [PRR_{48}] median 2.9, 95% CI: 0.26 - 5.8), but subsequent parasite regrowth is expected to occur. It is predicted that parasitaemia will return to the pre-dose baseline with a median of 7 days post-dosing (95% CI: 2.5 - 14). Additionally, modelling indicates that there is a 50% chance for a typical individual dosed with 20 mg to have a full parasitaemia profile above the lower limit of quantification (LLOQ) of the qPCR assay. Thus, a significant amount of data is expected to be generated at this dose level and three participants will be dosed with 20 mg MMV367 in Cohort 1.

Testing of 90 mg MMV367 is considered important because it is predicted to represent an “intermediate” dose level. That is, modelling indicates that 90 mg will result in faster parasite clearance (\log_{10} PRR_{48} median 3.6, 95% CI: 1.8 – 6.2) compared with 20 mg for a typical individual, while retaining a good chance of parasite regrowth occurring and thus contributing to refining the MMV367 EC_{50} estimate. Two participants will receive 90 mg MMV367 in Cohort 1.

Testing of 1500 mg MMV367 is required to characterise the PK/PD parameters across the full dose range, in particular the maximum killing rate (E_{max}). The chance of parasite regrowth occurring at this dose level is considered very low and thus data from this dose level will have a long duration of observable maximum killing rate ensuring a reliable estimation of the maximum clearance rate (E_{max}), however it is not anticipated to contribute to refining the estimate of the EC_{50} . Therefore, one participant dosed with 1500 mg is considered sufficient in the first cohort.

Dose selection for Cohort 2

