9.4 STATISTICAL ANALYSES

9.4.1 GENERAL APPROACH

Continuous variables will be summarised with the number of observations (non-missing values), mean, standard deviation (SD), median, quartiles, minimum and maximum. The minimum and maximum values will be presented to the same number of decimal places as recorded in the raw data. The mean, median and SD will be presented to one more decimal place than the raw data. Categorical variables will be summarised with the number of observations and the numbers and percent from each category. Percentages will be rounded to one decimal place, with the denominator being the number of participants in the relevant population with non-missing data. No missing data will be imputed. If required, confidence intervals (CIs) will be two sided and will use 95% confidence levels. Any analyses requiring significance testing will use a two-sided test at the 5% significance level.

The inoculation baseline will be defined as the last available assessment prior to administration of the malaria challenge agent. The IMP baseline will be defined as the last available assessment prior to the administration of the IMP. Unscheduled visits will be excluded from summary tables. Assessments conducted at Early Termination will be excluded from summary tables.

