The PRR_{48} will be estimated using the slope of the optimal fit of the log-linear relationship of the parasitaemia decay. The optimal fit will be derived using summarised replicate parasitaemia data, which have been cleaned by dealing with potential outliers, values below the limit of detection and non-detectable values. The optimal fit of the log-linear parasitaemia-by-time relationship is determined by using left and right censoring to systematically remove the potential lag phase and tail phase of the parasitaemia decay. The decay rate, estimated by the slope coefficient from the log-linear decay regression, will be calculated for each participant. The overall dose-specific PRR_{48} will be estimated with its 95% CI by calculating the weighted average slope estimate and corresponding standard error (SE) using an inverse-variance method. Only participants who have optimal regression models with appropriate fit contribute toward the dose-specific PRR_{48} . Details will be presented in the SAP.

The parasite clearance half-life ($PCt_{1/2}$) will be derived from the optimal decay rate. $PCt_{1/2}$ is a transformation of PRR_{48} into a per hour clearance rate. Details regarding the calculation of this parameter will be presented in the SAP.

PK parameters:

The following PK parameters will be determined using non-compartmental methods from plasma MMV367 concentration-time profiles: AUC_{last} , AUC_{inf} , C_{max} , t_{max} , $t_{1/2}$, CL/F , Vd/F and λ . When applicable, all PK variables (normally and log-normally distributed) will be summarized using arithmetic and geometric means, minimum, median, maximum, standard deviation (SD) and coefficient of variation (CV %) of arithmetic and geometric means. Summary tables showing the median and range for t_{max} and geometric mean and CV% for all other PK variables will be provided by dose.

Plasma concentration values below the lower limit of quantification will be set to zero. All mentioned parameters will be expressed as mean \pm SD, unless otherwise stated. Details regarding the calculation of this parameter will be presented in the SAP.

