[figure not shown]
The doses to be tested in Cohort 1 will be as follows:

MMV367 dose	20 mg	90 mg	1500 mg
Number of participants	3	2	1

The Safety Data Review Team (SDRT) will meet following the completion of Cohort 1 to review all safety, PK, and PD data. Doses to be tested in Cohort 2 will be informed by the results obtained in Cohort 1 and will be designed to refine the PK/PD parameter estimates. It may be necessary to test a dose lower than 20 mg in Cohort 2 if PK/PD parameters such as the EC50 were not sufficiently well estimated in Cohort 1. It may also be necessary to obtain additional data at the dose levels tested in Cohort 1. The maximum dose in Cohort 2 will not exceed 1500 mg. Specific doses, and the number of participants per dose, to be tested in Cohort 2 will be decided by the SDRT based on PK/PD simulations.

The SDRT will meet following the completion of Cohort 2 to review all safety, PK, and PD data. If the SDRT deems sufficient data has been obtained to achieve the primary endpoint (i.e., the PK/PD relationship of MMV367 has been appropriately characterized), a third cohort of participants will not be enrolled. If the SDRT deems further data is necessary, doses for Cohort 3 will be selected as described above for Cohort 2.

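### The Scheffé pairwise tests of dose-specific PRR48 use L - 1 degrees of freedom; the Scheffé reference is J - 1, so the stated rule is right only when the number of pairs equals the number of doses

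*SAP*

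**What the plan says.** SAP 11.1.2, under Comparison of Dose Specific PRR48, sets out two steps. Equation (9) defines an omnibus statistic Q_B across the J doses and refers it to chi-square on J - 1 degrees of freedom. The text then defines a contrast G of the dose-specific slopes, its variance v_G (the sum of c_j²/w_j), and Z_G = G/√v_G. It says that p-values for the L "pair-wise comparisons can be calculated using the Scheffe method, by comparing" Z_G² "to a chi-squared distribution with $L - 1$ degrees of freedom". It does not say whether L covers every pair or a selection.

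The number of doses is not fixed. Protocol 4.3 gives Cohort 1 three levels: "three participants will be dosed with 20 mg MMV367 in Cohort 1"; "Two participants will receive 90 mg MMV367 in Cohort 1"; and "one participant dosed with 1500 mg is considered sufficient in the first cohort". For later cohorts, SAP 3.1 says "It may be necessary to test a dose lower than 20 mg in Cohort 2", and it equally allows more data at the Cohort 1 doses. A dose can also drop out of the comparison, because Protocol 9.4.3 says "Only participants who have optimal regression models with appropriate fit contribute toward the dose-specific" PRR48.

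Protocol 9.4.1 sets the level: "Any analyses requiring significance testing will use a two-sided test at the 5% significance level".

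**The concern.** Scheffé's method protects all contrasts among J means at once. Its reference distribution is that of the largest Z_G² over every possible contrast. That depends on how many means there are, not on how many contrasts someone chooses to run. A rule based on L makes the p-value for one pair of doses change with the number of other pairs tested, and it gives the follow-up tests a different reference from the omnibus test they follow.

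What is at stake is how any statement that one dose clears parasites faster than another is judged. Depending on L and J, the rule as written is too strict, too lenient or impossible to compute.

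**Working it through.** **Inputs.** The definitions of Q_B, G, v_G and Z_G and the L - 1 rule come from SAP 11.1.2. Alpha of 0.05 comes from Protocol 9.4.1. J = 3 after Cohort 1 comes from Protocol 4.3. Values of J above 3 are assumptions shown as a range, since later doses are not fixed.

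**Step 1: the correct degrees of freedom, from the SAP's own definitions.** Write b_j for the weighted slope at dose j and b for the weighted grand mean. For any contrast (c_j summing to zero), G = Σ c_j b_j = Σ c_j (b_j - b). By the Cauchy–Schwarz inequality,

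G² ≤ (Σ c_j²/w_j) × (Σ w_j (b_j - b)²) = v_G × Q_B,

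so Z_G² ≤ Q_B. Equality holds at c_j = w_j (b_j - b), which is a valid contrast because b is the weighted mean. The maximum of Z_G² over all contrasts is therefore Q_B, which Equation (9) refers to J - 1 degrees of freedom. A numerical check with equal weights for J = 3 to 6 confirmed the equality.

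**Step 2: when L - 1 agrees.** L - 1 = J - 1 only if L = J. For all pairs, L = J(J - 1)/2, and setting this equal to J gives J = 3.

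**Step 3: all pairs, 5% critical values for Z_G².**

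| J | L | SAP df (L - 1) | Scheffé df (J - 1) | SAP critical value | Scheffé critical value | SAP p-value at the Scheffé 5% limit |
|---|---|---|---|---|---|---|
| 2 | 1 | 0 | 1 | none | 3.84 | none |
| 3 | 3 | 2 | 2 | 5.99 | 5.99 | 0.05 |
| 4 | 6 | 5 | 3 | 11.07 | 7.81 | 0.17 |
| 5 | 10 | 9 | 4 | 16.92 | 9.49 | 0.39 |
| 6 | 15 | 14 | 5 | 23.68 | 11.07 | 0.68 |

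For example, at J = 4 with Z_G = 3.0 (Z_G² = 9.00), the SAP rule gives p = 0.109 and Scheffé gives 0.029.

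**Step 4: error rate and power, all pairs.** These come from 200,000 simulated data sets with equal weights treated as known. Power is for one pair with expected Z of 3.5.

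| J | Family-wise error, SAP | Family-wise error, Scheffé | Power, SAP | Power, Scheffé |
|---|---|---|---|---|
| 4 | 0.005 | 0.026 | 57% | 76% |
| 5 | 0.0004 | 0.018 | 27% | 66% |

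**Step 5: a selection of pairs.**
- L = 1: zero degrees of freedom, so no p-value exists. This also happens if exclusions leave only two doses.
- L = 2: one degree of freedom, critical value 3.84, the same as an unadjusted test. Two pre-specified pairs span two dimensions, so the Scheffé-type limit is 5.99 (at J = 3 this is also the full bound). Simulated family-wise error with 3.84, for two pairs sharing a dose, is about 0.09 at both J = 3 and J = 4. If the two pairs are picked after seeing the data, the full J - 1 bound applies: 7.81 at J = 4, 9.49 at J = 5.
- L = 3 at J = 4 (each other dose against one reference): 5.99 is used instead of 7.81, but simulated family-wise error is about 0.038, still below 0.05.
- L = J, such as four pairs among four doses: the SAP rule gives the right degrees of freedom.

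**The case against.** The strongest reply is that little depends on this. SAP section 4 describes the approach to all endpoints as descriptive, and Protocol 9.1 states no hypothesis for the primary objective. Protocol 9.4.3 plans dose-specific PRR48 with confidence intervals and no test between doses. The SAP offers the pairwise tests as optional post hoc work, and neither the report contents in SAP 11.1.3 nor Table A lists any pairwise output. Later doses are chosen from PK/PD simulations, not from these p-values. All of this stands, and it limits the weight of the point.

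It can also be said that with the only doses fixed so far (three) and all pairs tested, the rule gives the right answer. That is true, but the SAP fixes neither the final number of doses nor the pairs.

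One could argue that L was meant as the number of doses. The text attaches L to the pairwise comparisons and already uses J for doses; if doses were intended, the symbol still needs correcting.

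A reader might infer that the p-values are wrong whenever there are not exactly three doses. The documents do not support this, because it assumes that all pairs are tested: L = J is right at any J, and J = 3 is wrong if only one or two pairs are run. Nor do they make four or more doses likely. A new level is possible, but repeating tested doses is equally provided for, Cohort 3 is conditional, and poor fits can reduce J.

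**Conclusion.** The rule is wrong as written: it departs from the Scheffé reference whenever L differs from J. If a dose level is added and all pairs are tested, the critical value is too high (11.07 against 7.81 at J = 4; 16.92 against 9.49 at J = 5). A reader might take this as a risk of false positive dose differences, but in that case the error is conservative: power is lost and type I error is not inflated. The lenient case needs a small selection of pairs, clearest at L = 2, where there is no adjustment at all. With a single pair the test cannot be computed.

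The derivation of J - 1 uses only the SAP's definitions and the chi-square reference in Equation (9). The error rates and power figures also assume equal weights, and the values of J above 3 are illustrations. This should be fixed but is not critical. The primary PK/PD analysis, dose-specific PRR48 with its intervals, the clearance half-life and the omnibus test do not use the rule.

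**What to change.** In SAP 11.1.2, replace L - 1 with J - 1, and define J as the number of doses in Equation (9) with at least one participant with an appropriate fit. Add a sentence stating which pairs will be compared: all of them, or a named set fixed before the data are seen. The cost is one symbol, one sentence and one line of code, with no effect on trial conduct. SAP section 2 places finalisation before database lock, so the change belongs before that point.
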